Q2RESEARCH PROTOCOL TEMPLATE INVESTIGATOR INITIATED TREATMENT TRIALS

Title of Project: Treatment of Post-Operative Sinonasal Polyposis with Topical

Furosemide

Principal Investigator: [name], Otolaryngology

Co-Investigators: [name] MD, Otolaryngology; [name],

Otolaryngology; [name], Otolaryngology; [name] PharmD

Abstract

Prior studies have suggested that topical furosemide may reduce the recurrence of sinonasal polyposis following sinus surgery. This project aims to further investigate that claim through a blinded randomized controlled clinical trial following patients who undergo functional sinus surgery for chronic rhinosinusitis with sinonasal polyposis (CRSwP) by randomly assigning participants to receive topical furosemide versus placebo nasal irrigation for 6 weeks post operatively. Outcomes would be compared at 6 months through endoscopic grading scores using Lund Kennedy and Meltzer scores as well as Sino-Nasal Outcome Test (SNOT-22) scores to measure the rate and degree of recurrence and impact on symptoms in the treatment group versus placebo.

A. Specific Aims

State the hypothesis and specific aims. List the long-term objectives and what the proposed research will accomplish.

Hypothesis: Topical furosemide prevents the recurrence of sinonasal polyposis following endoscopic sinus surgery in CRSwP patients

Through investigating this hypothesis, the group aims to provide evidence for treating CRSwP patients with a safe and effective medical therapy to prevent or reduce the recurrence of sinonasal polyposis after sinus surgery. If proven effective in the immediate post operative period, the research would lead to further research aimed at the long term effects of therapy in CRSwP patients to develop a protocol to prevent the recurrence of sinonasal polyps and potentially change the post-operative management of CRSwP patients.

B. Background and Significance

Nasal polyposis is a common disease of the mucous membranes in the nose and the paranasal sinuses that develops as a reaction to a variety of stimuli including allergens and various microbes.⁴ They usually occur in chronic rhinosinusitis associated with allergy, inflammation, and submucosal edema.⁵ Nasal polyps are associated with nasal congestion, postnasal drip, runny nose, sneezing and olfactory disorder that greatly impact patient's quality of life.⁶ Management of nasal polyposis in this patient population is extremely difficult and functional endoscopic sinus surgery remains a mainstay of treatment in those patients who

have failed medical therapy. That said, there are high rates of recurrence after surgery. Recent studies have suggested that nasal furosemide may be effective in reducing the recurrence of polyps after sinus surgery by affecting inflammation and edema post operatively. However, evidence is limited and insufficient with further investigations required. This study aims to provide evidence for treating CRS patients with a safe and effective medical therapy to prevent or reduce the recurrence of sinonasal polyposis after sinus surgery and limit the morbidity of their recurrence in this group of patients as well as the limit the risks of corticosteroid steroid therapy used currently.

C. Preliminary Studies/Progress Report

Provide an account of preliminary studies and/or information that establishes the experience and competence of the investigator to pursue the protocol. (suggested length less than ½ page)

Our principal investigators, Drs. [name], [name] and [name] have extensive experience and specialized training in treating patients with chronic sinusitis and nasal polyposis. At this time, there is no standardized treatment for these patients and they often require multiple rounds of oral steroids which have associated side effects. The goal of this study is to investigate whether or not the novel use of topical intranasal furosemide can help decrease the use of oral steroids for this population. Collectively, we have the the equipment, expertise and knowledge-base to follow through with this study.

D. Research Design and Methods

Describe the research design and procedures to be used (what, when, how) Include the duration of participation and early termination criteria. Provide a flow diagram or timetable. Procedures, situations, or materials that may be hazardous to personnel and the relevant precautions, should be outlined here. (suggested length not more than 2 pages)

Through a blinded randomized controlled clinical trial, the recurrence rates of nasal polyps in patients with chronic rhinosinusitis with polyps who are undergoing sinus surgery will be compared through their response to therapy with topical furosemide versus placebo. Eligible patients will be recruited through the Otolaryngology Department at Thomas Jefferson University Hospital. During pre-operative clinical visits, eligible patients will be selected and provided the option to participate in the study.

Topical sinus medications have been administered via Mucosal Atomization Device (MAD) in the treatment of chronic rhinosinusitis. Kanowitz et al studied the use of budesonide respules administered via MAD in refractory postoperative

rhinosinusitis⁹. A separate study found that medication administered via the MAD resulted in distribution to the maxillary sinus, ethmoid cavity, and frontal recess post endoscopic sinus surgery¹⁰.

When administering furosemide via the MAD, a total daily dose used in a previous nasal spray trial of 300 mcg was utilized¹¹. Patients may administer 75 mcg/0.3 ml to each nostril twice daily to result in the total daily dose of 300 mcg. The volume of 0.3 ml to each nostril is the volume recommended by the manufacturer for intranasal administration via the MAD nasal device.

Performing nasal atomization with 150 mcg twice daily would results in a total exposure of 300 mcg of furosemide daily. Following intranasal administration, a drug may enter systemic circulation through direct local absorption in the nasal mucosa or oral absorption of the swallowed medication¹². When administering intravenous furosemide it has a threshold dose. No diuretic effect is evident at any dose lower than the threshold dose. The threshold dose for intravenous furosemide is 10 mg in a population with normal renal function¹³. Extrapolating this data, a 300 mcg exposure of furosemide should not result in diuresis. A portion of the drug may also be cleared from the sinuses into the throat and swallowed, making it available for gastrointestinal absorption. Furosemide oral solution has a bioavailability of 60%, of that from an intravenous injection of furosemide¹⁴. Therefore swallowed medication should not result in therapeutic levels of furosemide.

After obtaining consent, selected patients will be randomized into 2 groups using the balance block randomization method to either treatment group or placebo group and be scheduled for surgery. Balance block randomization involves the preparation of 4 sheets of paper, writing on 2 sheets "F" for "furosemide" and on 2 sheets "P" for "placebo". The paper sheets will be pooled, placed in a container, and randomly drawn 1 at a time without replacement until all sheets were drawn. The paper sheets will then be placed back into the container and the selection process will be repeated until the sample size is reached. The study investigators will be blinded to the selection process and the randomization will be carried out by the clinical research nurse. A total of 100 patients will be enrolled in the study.

Pre-operatively all patients will receive a 5 day course of 40 mg prednisone, at least one week of and intranasal steroid, and saline irrigation. During a preoperative clinical visit, the degree of sinonasal polyposis will be graded through the Lund Kennedy and Meltzer endoscopic scoring system as well as degree of symptoms through SNOT-22 scores. Also, a demonstration and instructional sheet for how to administer the nasal spray will be distributed at this time.

Then, patients will undergo functional endoscopic surgery as scheduled.

Immediately post-operatively, patients will begin a 6 week course of twice a day nasal spray If assigned to the treatment group they will receive 300 micrograms of furosemide daily. If assigned to the placebo group, they will receive saline. The clinical research nurse will distribute an unmarked bottle of nasal spray to the study patients either in a pre-operative clinical visit or in the recovery room on the day of surgery. Creation of the study drug will be done by AdvancedRx of Plymouth Meeting, Pa. The department research nurse will store and distribute the study drug to the subjects. Post-operatively, patients will also receive a 40mg prednisone taper (40mg for 3 day, 30mg for 3 days, 20 mg for 3 days, 10 mg for 3 days), nasal saline and a 5-day course of omnicef and at least a 6 week course of intranasal corticosteroid spray. Patients will be given a diary to record any doses that were missed.

Patients taking aminoglycosides will be excluded from this trial as furosemide may increase the ototoxic potential of aminoglycosides. Study subjects who require aminoglycoside use during the study treatment period will be instructed to discontinue taking the study drug and will be removed from the study.

Post-operative visits will be scheduled at 1 week, 3 week, 2 month, 4 month and 6 month intervals. The post-operative visits may be scheduled within 4 days of the scheduled interval. Post-operatively, the degree of nasal polyposis will again be graded through the Lund Kennedy and Meltzer endoscopic scoring system as well as degree of symptoms through SNOT-22 scores. These scores will be obtained at the 2, 4 and 6 month visit.

The duration of participation for the study will be 6 months. Early termination criteria are serious adverse reactions, inability to recruit or adequately enroll an adequate number of patients, problems arise in the study medicine's stability or manufacturing and new toxicological findings that affect the benefit-to-risk ratio.

E. Statistical Methods

If not a pilot study, provide biostatistical design, power calculations determining the number of participants , and the proposed analysis. (suggested length: $\frac{1}{2}$ page)

Based on prior randomized controlled clinical trials, the study is powered to achieve at least 80% power. Based on the results published by Hashemian et al.¹, Group sample sizes of 40 in ctrl and 40 in treat achieve 95% power to detect a difference of 38% vs. 79% using two-sided Fisher's Exact Test with significance level 5%. Also based on results published by Passali et al.², group sample sizes of 47 in ctrl and 47 in treat achieve 80% power to detect a difference of 30% vs. 6% using two-sided Fisher's Exact Test with significance level 5%.

The primary outcomes will be compared through the independent t test for continuous variables and the Fischer exact test for nominal variables. All statistical analyses will be performed at a significance level of 0.05.

F. Gender/Minority/Pediatric Inclusion for Research

All protocols must include documentation of the inclusion of women and minorities in the research protocol. If women and minorities are not to be included, provide rationale for exclusion.

The study will include women and minorities.

G. Human Subjects

1. Provide number, age range, and health status of the subject population. List criteria for inclusion or exclusion.

100 patients, 18 to 65 years old, chronic rhinosinusitis with sinonasasl polyposis

Inclusion Criteria:

Patients with chronic rhinosinusitis and sinonasal polyposis who are candidates for functional endoscopic sinus surgery

Exclusion Criteria:

Hypersensitivity to furosemide or sulfonamides, pregnancy, history of tinnitus, history of sensorineural hearing loss, poorly controlled diabetes, current diuretic therapy, known electrolyte disorder, currently taking aminoglycosides, BUN and creatinine levels out of the normal range, history of renal disease, allergy to sulfonamides.

2. Identify sources of research material in the form of specimens, records or data.

Patient medical record, physical exam findings (endoscopic scores), SNOT-22 questionnaire,

3. Describe plans for recruitment and consent procedures to be followed.

Patients will be recruited through clinical visits at the Department of Otolaryngology at Thomas Jefferson University Hospital. Informed consent will be obtained at those clinical visits. Potential subjects will be informed of the research and provided a copy of the consent at their office visit with the physician. Either the principal investigator, co-investigators, or the department's research nurse will conduct the consent interview. At that time, one of the investigators will present the study to the subject. The subject will be allowed to read the consent and ask questions. The subject may also have the consent form read aloud to them. The investigator conducting the consent interview will ensure that all sections of the consent form are reviewed with the subject. Subjects will be provided with as much time as they need to review the consent form. If they do not want to sign at the time of this visit, they may bring the consent home with them and come back at a later time to sign.

4. Describe risks and assess likelihood and seriousness.

Since the study involves the standard of care for CRSwP undergoing sinus surgery, the study's risk are limited to the study drug, topical furosemide. As an FDA approved medicine, oral/intravenous furosemide has been shown to have

the following risks: dehydration and fluid/electrolyte imbalance (hyponatremia, hypochloremic alkalosis, hypokalemia, hypomagnesemia or hypocalcemia): dryness of mouth, thirst, weakness, lethargy, drowsiness, restlessness, muscle pains or cramps, muscular fatigue, hypotension, oliguria, tachycardia, arrhythmia, or gastrointestinal disturbances such as nausea and vomiting). In addition furosemide has been shown to cause tinnitus and sensorineural hearing loss, dizziness, headache and blurred vision. Other reactions in decreasing order include hyperglycemia, glycosuria, hyperuricemia, muscle spasm, weakness, restlessness, urinary bladder spasm, thrombophlebitis and fever. Some hematologic and dermatologic reactions have also been reported. Patients allergic to sulfonamides may also be allergic to furosemide due to its incorporated sulfa moiety. That said, review of clinical trials of inhaled furosemide in acute and chronic asthma indicates that it does not induce significant side effects and no diuretic effect has been reported.8 In prior studies with topical nasal spray use, topical furosemide has be shown have a limited side effect profile including nasal irritation and constipation. It is unlikely that patients enrolled in the study will have side effects or adverse events based on prior studies and if they do the adverse effects will likely be minor.

- 5. Describe procedures for protecting against or minimizing potential risks. Patients will be screened closely using the inclusion/exclusion criteria involving health status and prior sensitivity reactions to furosemide or sulfonamides. Also, the patients will be followed closely for adverse reactions during the post-operative period with visits at 1 week, 3 week, 2 month, 4 month and 6 month intervals. Any adverse effect will be documented and if serious appropriate intervention or discontinuation of study drug will be addressed.
- 6. Describe potential benefits and importance to the subjects and others. Topical furosemide nasal spray may limit the recurrence of nasal polyposis. If proven effective, it would provide support for a novel use of a well known and affordable drug to create a safe and effective medical therapy to limit the morbidity of recurrence of polyps and multiple surgical procedures as well as an alternative to harmful effects of current therapies involving chronic systemic and topic steroid use.
- 7. Discuss why risks are reasonable in relation to benefits. Given the minimal risks of topical furosemide, close follow up with monitoring and limited length of a 2-month treatment course in a 6 month study with the potential benefit of preventing the recurrence of nasal polyposis in this complicated subset of patients, the risks of the study are reasonable in relation to the benefits. If proven effective, this study may change the post-operative management of nasal polyposis and provide patients a safe and effective medical therapy to prevent and limit the morbidity of the recurrence of nasal polyps in chronic rhinosinusitis patients.

H. Data and Safety Monitoring Plan

All protocols that pose greater than minimal risk must have a Data and Safety Monitoring Plan (see DHSP policy G 616 "Independent Monitoring of Investigator-Initiated Clinical Trials."

- 1. Describe the Data and Safety Monitoring Plan (DSMP)
 - a. reporting mechanisms for adverse events to the IRB, FDA, and NIH. Investigators will follow all guidelines for reporting to IRB.
 - b. adverse event (AE) grading Adverse events will be graded by investigators using the CTCAE v.4.
 - c. plan for unanticipated AE reporting Unanticipated adverse events will be reported to the IRB per the reporting guidelines.
 - d. plan for annual reporting of AEs
 Annual reporting of AEs will be done at the time of continuing review.
 - e. interim efficacy analysis where appropriate If not, just put n/a, no interim efficacy analysis will be done.
- 2. If applicable, describe the Data and Safety Monitoring Board (DSMB) that will be responsible for monitoring the study. Indicate Chair, members, areas of expertise, frequency of meetings, distribution of reports. There is no DSMB for this study.

I. Literature Cited

List only literature cited within the text. (suggested length: no more than 12 references)

Date	5/10/2018
Version	6.0

Research Protocol Template, 11/15/2010

- ⁶ P.S. Batra, L. Tong, M.J. Citardi Analysis of comorbidities and objective parameters in refractory chronic rhinosinusitis Laryngoscope, 123 (Suppl 7) (2013), pp. S1–S11
- ⁷ Wynn, R. and Har-El, G. (2004), Recurrence Rates after Endoscopic Sinus Surgery for Massive Sinus Polyposis. The Laryngoscope, 114: 811–813. doi:10.1097/00005537-200405000-00004

 ⁸ Niven AS, Argyros G (2003) Alternate treatments in asthma. Chest 123(4):1254–1265

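### Section D has a research nurse draw from visible fixed blocks of four and G.3 lets a research nurse take consent; if they are one person, allocation is partly foreseeable, with probably small bias and a cheap fix.

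*Combined protocol and SAP*

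**What the plan says.** Section D (Research Design and Methods) describes a container with four sheets, two for furosemide and two for placebo, "randomly drawn 1 at a time without replacement until all sheets were drawn". The container is then refilled and the process repeats until 100 patients are enrolled. On timing it says: "After obtaining consent, selected patients will be randomized into 2 groups". On roles it says: "The study investigators will be blinded to the selection process and the randomization will be carried out by the clinical research nurse".

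The same section names the nurse in two ways for one dispensing task: "The clinical research nurse will distribute an unmarked bottle of nasal spray to the study patients", and shortly afterwards, "The department research nurse will store and distribute the study drug to the subjects".

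Section G.3 (recruitment and consent) lists the principal investigator, the co-investigators and the department's nurse as alternatives for taking consent; the last of these is covered by the words "research nurse will conduct the consent interview". It also says that "one of the investigators will present the study to the subject", and that patients may take the form home and sign later.

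**The concern.** The person drawing from a block of known composition can see or remember what is left in it. Drawing after consent protects the current patient's assignment. It does not protect the next one, because the draws already made in the block may fix it before the next patient is approached.

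The protocol plainly intends concealment, since it blinds the investigators to the selection process. That blinding does not extend to the nurse who draws, and no passage separates drawing from consent. If the clinical and the department research nurse are the same person, a permitted consenter could foresee some allocations and so affect who is consented, or when. Selection bias of this kind is hard to detect or correct afterwards.

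**Working it through.** **The plan's own figures.** The documents give no predictability figure. The only computed figures are the power statements in section E, and this point needs just one planned difference from them: 30% vs 6%, which is 24 points. For reference, exact two-sided Fisher power is 95.6% at 40 per arm for 38% vs 79% (stated 95%). For 30% vs 6%, the continuity-corrected formula gives 47 per arm for 80% power, as stated; exact Fisher power at 47 per arm is 82.5%.

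**Step 1: what the person drawing can foresee.** Inputs from section D: block of four, two sheets per arm, no replacement. Assumption: one sheet drawn per consented patient. There are 6 equally likely orderings.

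- Chance that the assignment is already certain, by position: 0, 0, 1/3 (the first two were alike), 1. Mean = (0 + 0 + 1/3 + 1)/4 = 1/3.
- Chance that the best guess is right, by position: 1/2, 2/3, 2/3, 1. Mean = 2.833/4 = 70.8%, against 50% under concealment.
- With 100 patients (25 blocks), the expected number of certain assignments is 33.3. The possible range is 25 to 50, because each block yields one or two.

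**Step 2: what could be acted on.** The documents give neither the share of patients whose enrolment the nurse influences nor how far patients steered to the two arms would differ in recurrence risk. Both are assumed:

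- Share: 10%, or one third as a high-end case. One third is an even split among the three permitted groups of consenters and is probably too high.
- Risk gap: 10 to 20 points, with every influenced patient fully steered.

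Certain assignments open to action = 100 × 1/3 × share: 3.3 at 10%, 11.1 at one third.

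Shift between arms, acting on certain assignments only = share × gap × 1/3.
Shift between arms, acting on best guesses = share × gap × (2 × 0.7083 − 1) = share × gap × 0.417.

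| Share | Gap (points) | Certain only (points) | Best guess (points) |
|---|---|---|---|
| 10% | 10 | 0.33 | 0.42 |
| 10% | 20 | 0.67 | 0.83 |
| 1/3 | 10 | 1.11 | 1.39 |
| 1/3 | 20 | 2.22 | 2.78 |

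Simulating 60,000 blocks per case agreed to within 0.01 points.

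**Step 3: effect on the test.** Exact rejection rate of the two-sided 5% Fisher test with 50 per arm and no treatment effect, with risks set at 30% (a section E figure) plus and minus half the shift:

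- no shift: 3.07%
- shift of 0.83 points: 3.13%
- shift of 2.78 points: 3.83%

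The rate stays below 5% because Fisher's test is conservative at this size. Section E also plans t tests for continuous primary outcomes. These start at about 5% with no such margin, so the reassurance does not carry over to them. The documents give no standard deviation from which to size that effect.

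**The case against.** The strongest reply is that the opportunity is narrow. Randomization follows consent. The draw is delegated away from the investigators, and the bottle is unmarked. Patients hear of the study at a physician visit, an investigator presents it, and G.3 goes on to say: "The investigator conducting the consent interview will ensure that all sections of the consent form are reviewed with the subject". Most exclusion criteria are history, medication or laboratory items, which leaves little discretion over eligibility. Taking the form home is the patient's choice, so it leaves the order of signing open without showing that the nurse controls it. All of this stands, and it is why the likely bias is small. It does not close the gap, because G.3 still names the nurse as a permitted consenter and the nurse is not among those blinded.

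A reader might infer that a third of the trial is exposed to selection bias. The documents do not support that. One third is what the person drawing can foresee, whoever takes consent; exposure also requires influence over enrolment. A reader might also infer that the overlap of roles is established. It is not: the two titles share a task but are never equated, and if they are different people the overlap disappears.

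The one-third figure itself depends on one draw per patient. The statement that randomization follows consent favours that reading, but the wording does not exclude drawing a block ahead, in which case the nurse would know more.

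**Conclusion.** The point holds as a minor gap in allocation concealment. It is conditional on the two nurse titles being one person and, for the figures, on one sheet being drawn per patient. That nurse would know one third of assignments on average, but on the assumed inputs could use that certainty for only about 3 to 11 of 100 patients. The resulting shift is roughly 0.3 to 2.8 points, with the upper end requiring best-guess steering of a full third of patients. Against a planned difference of 24 points this would be unlikely to decide the result. The share, the risk gap and complete steering are all assumptions, so these figures illustrate scale and do not estimate a bias. What the documents do establish is an unresolved overlap of roles, which is worth removing because doing so costs almost nothing.

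**What to change.** - **G.3:** amend the sentence that lists who may conduct the consent interview, so that anyone who draws or holds the allocation sequence takes no part in eligibility decisions or consent. The existing sentence must itself change; a new sentence placed beside it, or added only in section D, could contradict it.
- **Section D:** state whether the clinical research nurse and the department research nurse are the same role.

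Consent by investigators alone is already permitted, so no new staff or procedure is needed. The cost is that this nurse can no longer take consent. For whoever does, assignments known in advance fall from one third to none and the best guess from 70.8% to 50%, provided the stated blinding of the investigators holds.

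Optionally, if the compounding pharmacy agrees, it could hold a computer-generated list and supply sequentially numbered, otherwise identical bottles, so that the nurse never holds the code. Section D says only that the pharmacy creates the drug, so this would need an agreement and some coordination. The fix does not depend on it.

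### On the 6-week course, about half of dosing has no planned real-time check for adverse effects or new medicines, and the diary is described only as a record of missed doses

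*Combined protocol and SAP*

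**What the plan says.** Section D states that "patients will begin a 6 week course of twice a day nasal spray", starting immediately after surgery. On contacts it says: "Post-operative visits will be scheduled at 1 week, 3 week, 2 month, 4 month and 6 month intervals". It adds: "The post-operative visits may be scheduled within 4 days of the scheduled interval". No telephone call or other contact is listed between week 3 and month 2. SNOT-22 is scored at 2, 4 and 6 months, so no symptom questionnaire falls within the 6 weeks.

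The diary has one described purpose: "Patients will be given a diary to record any doses that were missed".

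Section D also carries a drug-specific safety rule, with ototoxicity as its reason: "Study subjects who require aminoglycoside use during the study treatment period will be instructed to discontinue taking the study drug". Such patients are also removed from the study. How staff would learn of the aminoglycoside is not stated.

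Section G, item 4, lists the known risks of oral and intravenous furosemide, including fluid and electrolyte disturbance, and says: "In addition furosemide has been shown to cause tinnitus and sensorineural hearing loss". Item 5 names the same five visits as the follow-up for adverse reactions. It says that adverse effects will be recorded and that stopping study drug will be considered if they are serious. Item 7 argues that the risk is acceptable: "Given the minimal risks of topical furosemide, close follow up with monitoring". The same sentence describes the "limited length of a 2-month treatment course in a 6 month study", which does not match the 6 weeks in the Abstract and section D.

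**The concern.** The aminoglycoside rule and the provision to consider stopping study drug for a serious effect can act only if someone on the study team knows of the problem while the patient is still dosing. After week 3, nothing in the described schedule or diary would tell them. Item 7 nevertheless relies on close follow-up as part of the case that the risks are reasonable.

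The second issue is what the safety data will be worth. Item 4 expects any effects to be minor. Mild, transient effects are the ones most easily forgotten by a visit weeks later. If they are lost in both arms, the recorded rates are too low and a comparison of the arms has fewer events to work with. A low count would then be weak support for the safe therapy that section A hopes to establish, because it could reflect the schedule as much as the drug. No efficacy result is affected.

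**Working it through.** The documents give no figure for the share of dosing without contact, so there is none to reproduce. The check is calendar arithmetic.

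**Inputs**
- Course length: 6 weeks = 42 days from surgery (section D).
- Last on-treatment visit: week 3 = day 21. With the 4-day window read as plus or minus 4, this is day 17 to 25 (section D).
- Next visit: month 2 (section D). The documents do not define a month, so day 56, day 60 and day 61 (2 × 30.4) are all tried, each plus or minus 4.

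**Share of dosing after the last on-treatment visit** = (42 − visit day) / 42
- Visit on day 21: 21 / 42 = 50%
- Visit on day 25: 17 / 42 = 40%
- Visit on day 17: 25 / 42 = 60%

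**Delay from last dose to the month-2 visit** = visit day − 42
- Month 2 as day 56 (52 to 60): 10 to 18 days
- Month 2 as day 60 (56 to 64): 14 to 22 days
- Month 2 as day 61 (57 to 65): 15 to 23 days

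On a 6-week course, the month-2 visit therefore falls after dosing on every reading, by 10 to 23 days.

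**If the course were 2 months, as in section G, item 7**
- Counted as 56 days: (56 − 21) / 56 = 62.5%
- Counted as 60.9 days: (60.9 − 21) / 60.9 = 65.5%
- With the visit windows, the share lies between about 52% and 72%. The low end is (56.9 − 25) / 60.9 and the high end is (60.9 − 17) / 60.9.
- If course and visit are counted in the same way, the month-2 visit falls within 4 days of the last dose.

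So a 2-month course raises the uncovered share but largely removes the recall delay after the last dose. The gap after week 3 exists on both readings, but its size and consequences differ.

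**What could fill the gap.** Three sources could inform staff between week 3 and the end of dosing: a visit (none listed), a diary entry (missed doses are the only stated content) or an unprompted report by the patient (possible, but not described). Section H provides adverse event grading and reporting but adds no patient contact, and it states that there is no DSMB.

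**The case against.** A reader might infer that ear and systemic risks go unmonitored for half of exposure. The documents do not support that. Section G, item 5, follows patients for adverse reactions at all five visits, including month 2, and provides for adverse effects to be recorded. Section H adds CTCAE grading and IRB reporting. Late-course events can therefore be captured, though retrospectively.

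A reader might also infer that the aminoglycoside rule cannot operate after week 3. That goes too far. A patient may volunteer the information. The consent pages are not in the available copy, the content of the instruction sheet for the spray is not given, and either may tell patients whom to call. It can be said only that the protocol text describes no such step. Such an instruction, if it exists, would not by itself make the diary collect dated symptoms or medicines.

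The size of the risk is also fairly contested. The ear and electrolyte list is given for oral and intravenous furosemide; for topical nasal use, item 4 reports nasal irritation and constipation. Section D sets 300 mcg daily against a 10 mg intravenous threshold for diuresis (0.3 / 10 = 3%) and expects none. Patients with a history of tinnitus or sensorineural hearing loss, a known electrolyte disorder, current diuretics or abnormal BUN or creatinine are excluded. This stands as regards systemic effects. The diuresis argument does not address hearing, and the protocol kept the aminoglycoside rule at this dose.

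Finally, the contrast between the two halves of the course should not be overdrawn. No hearing or laboratory check is listed at weeks 1 or 3 either. What those visits offer is a contemporaneous contact, and that is what is missing afterwards.

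**Conclusion.** The point holds as a weakness in safety ascertainment. On the 6-week course, 17 to 25 of 42 dosing days (40% to 60%, nominally 50%) have no planned real-time check for adverse effects or new medicines. What happens in that period is left to recall at month 2, about 10 to 23 days after the last dose, and no stated step would trigger the aminoglycoside rule during it.

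This assumes that dosing and visits are counted from surgery, that the window is plus or minus 4 days, that two months means 56 to 61 days, and that the diary holds no more than section D describes. If the 2-month course applies, the uncovered share rises to about 63% to 66% (about 52% to 72% with the windows), and the month-2 visit falls near the end of dosing. It is a low-cost improvement worth making, not a flaw that undermines the trial.

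**What to change.** In section D, extend the existing diary to record, with dates, any new symptom (including ringing or hearing change, dizziness and nasal irritation) and any new prescription medicine. Ask patients to report these promptly to the study team during dosing.

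A telephone call is optional. If one is added, place it between week 3 and the end of dosing; a call once the course is over cannot bring the aminoglycoside rule into play. Have a blinded investigator elicit and grade adverse events. Under section D the clinical research nurse carries out the randomization, so that role should not also ascertain adverse events.

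Reconcile the 6-week course (Abstract and section D) with the 2-month course (section G, item 7).

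The cost is a few diary lines and a short amendment, plus 100 calls if one is made per patient. The downside is slightly more patient burden and more minor adverse events recorded in both arms. No visit, procedure or treatment rule needs to change for the diary extension.
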